1 BACKGROUND AND RATIONALE

Globally, colorectal cancer (CRC) is the third most common cancer in men and women, with an estimated 1.4 million new cases and 694,000 deaths in 2012; the majority of which occur in developed countries. In Europe, CRC is the second most common cancer, with an estimated 447,136 new cases and 214,855 deaths in 2012.¹ Approximately one-quarter of patients with CRC have metastatic disease at the time of initial diagnosis and half of the patients develop metastatic disease following their initial diagnosis.²

Metastases in CRC can be synchronous (detected prior/during surgery of the primary tumor or within 3 to 12 months following initial intervention) or metachronous (discovered more than 1 year after surgical resection of the primary tumor). Synchronous metastases are usually associated with a locally advanced CRC following a greater metastatic burden and a poor outcome.¹⁸ The most frequently involved organs in metastatic CRC (mCRC) are the liver, peritoneum, lungs, bone and brain. The liver is often the single site of metastasis in CRC at the time of initial diagnosis (20% to 25% of cases) or after resection of the primary tumor (40% of cases).¹⁹ Peritoneal metastases are detected in 4% to 19% of patients after surgical resection of the primary tumor, and have survival rates of 5-24 months.²⁰ Lung metastases occur in 10% to 30% of patients at 5-60 months after resection of the primary tumor.²¹ The incidence of bone metastases in CRC varies from 6% to 10%, with a median time of detection of 11-21 months after resection of the primary tumor.²² Brain metastases occur in 2% to 12% of CRC patients during the course of the disease, with a median survival rate ranging from 2.8 to 6 months without surgery and from 6 to 10 months after metastatic resection.²³ Recent research suggests that certain gene mutations, such as Kirsten Rat Sarcoma Viral Oncogene (KRAS), B-Raf proto-oncogene (BRAF), phosphatidylinositol 3-kinase catalytic subunit (PIK3CA), and Neuroblastoma RAS viral oncogene homolog (NRAS) oncogenes, may affect the metastatic behavior of tumors and the patterns of metastatic spread.

Treatment options for mCRC patients

First-line treatment in patients with mCRC includes a combination of chemotherapy regimens and biological agents.^{3 4} Systemic anti-cancer therapy (SACT) is the main treatment option where combination chemotherapy remains the consensus standard of care. Current guidelines advocate the doublet combinations with oxaliplatin (5-fluorouracil [5-FU], leucovorin, and oxaliplatin [FOLFOX]) or irinotecan (5-FU, leucovorin, and irinotecan [FOLFIRI]) based regimens.² These regimens are shown to be superior to combination of 5-FU and folinic acid alone.²⁴

Targeted therapy, including vascular endothelial growth factor (VEGF) inhibitor bevacizumab or epidermal growth factor receptor (EGFR) monoclonal antibodies (cetuximab and panitumumab), is currently recommended by clinical guidelines as selective addition to the chemotherapy regimens, taking into account patient's RAS status.² Bevacizumab, when given in combination with chemotherapy has shown to significantly improve overall survival (OS) compared to chemotherapy alone.^{5 6} The survival benefit was retained in patients who continued using bevacizumab as a combination therapy, beyond first-line progression.⁷ Other biological agents such as cetuximab and panitumumab, both of which are EGFR monoclonal antibodies, have demonstrated benefits in survival, progression free survival (PFS) and response rate when used as first-line treatment of patients with wild-type KRAS (KRASwt) tumors in combination with FOLFIRI and FOLFOX when compared to chemotherapy alone, but not with other oxaliplatin-based regimens such as FLOX

(combination of fluorouracil, leucovorin and oxaliplatin) and CAPOX (combination of capecitabine and oxaliplatin).³⁻⁸

B-Raf proto-oncogene mutant colorectal cancer

BRAF encodes a serine/threonine protein kinase belonging to the RAS/RAF/mitogen activated protein kinase (MEK)/extracellular signal-regulated kinase (ERK) kinase pathway that has been implicated in pathophysiology proliferation, invasion, and metastasis in CRC.²⁵ Approximately 5% to 15% of CRC patients have a mutation in the BRAF gene resulting in a valine-to-glutamate change at the residue 600 (V600E), which is nearly always mutually exclusive with the RAS mutation.^{6-9,26}²⁷ Multiple clinical trials suggest that BRAF mutation is a poor prognostic factor for mCRC.^{10,12,28,29}

Metastatic CRC patients with BRAF mutation have median OS of 10 to 15 months compared to 21 to 35 months for patients with BRAF wild-type (BRAFwt) tumors.¹¹⁻¹³ Patients with BRAF mutation have more adverse histologic features, such as lymphatic invasion, mean number of lymph node metastases, perineural invasion, and high tumor budding.³⁰ Studies suggest that BRAF mutant mCRC is less likely to present liver-limited metastasis and is associated with increased incidence of peritoneal and distant lymph node involvement.^{12,29,31,32} This pattern of metastatic spread in BRAF mutant mCRC may contribute to the poor outcomes.^{12,33}

Considering the prognostic importance of BRAF mutation, the European Society of Medical Oncology and the National Comprehensive Cancer Network panel have recommended assessment of BRAF mutation status alongside RAS gene mutation status in mCRC patients.^{2,34}

Treatment options for BRAF mutant mCRC patients

To date, there is no agent specifically indicated for patients with BRAF mutant mCRC. Limited data from unplanned retrospective analysis of patients receiving first-line treatment have produced inconclusive results.³ Because RAS and BRAF^{V600E} mutations are almost always mutually exclusive, BRAF mutant mCRC patients are typically treated with standard of care regimens for KRASwt tumors, i.e., either oxaliplatin- or irinotecan-based SACT, with or without bevacizumab (anti-VEGF antibody) or cetuximab (anti-EGFR antibody) but with substantially poorer outcomes than patients with BRAFwt tumors.

A retrospective study reported no differences in PFS irrespective of whether oxaliplatin- or irinotecan-based chemotherapy was administered in the first-line setting in patients with BRAF mutant CRC (6.4 versus 5.4 months; P=0.99).¹⁴ There is insufficient evidence to conclude that BRAF is a predictive biomarker for irinotecan or oxaliplatin, as patients benefit regardless of their mutational status.

With regards to targeted agents, in a post-hoc analysis of a Phase 3 trial comparing bevacizumab-based chemotherapy with chemotherapy alone, it was reported that BRAF mutation status predicted poor survival overall but had no impact on bevacizumab benefit.³⁵ BRAF mutation status predictive value for response and benefit from EGFR-directed treatments, such as cetuximab, remain controversial.

Limited data from unplanned retrospective subset analyses of subjects with mCRC treated in the first-line setting suggest that, although a BRAF^{V600E} mutation confers a poor prognosis regardless of

treatment, subjects with disease characterized by this mutation may receive some benefit from the addition of cetuximab to front-line therapy.^{13 36}

Retrospective analyses of recent trials have suggested that *BRAF* mutations are not predictive of outcome with EGFR-directed therapies³⁷ in certain settings whereas other analyses have suggested that cetuximab and panitumumab are most active in subjects with *BRAF*wt mCRC^{26 38}. In a recent meta-analysis of 7 randomized controlled trials in which subjects received panitumumab or cetuximab in different lines of therapy, and with a range of background chemotherapy, no significant interaction was noted between the benefits of anti-EGFR therapy (measured as OS and PFS) and the presence of *BRAF* mutations. These results suggest that anti-EGFR therapy may have benefit for subjects with *BRAF*^{V600E} CRC.

In a retrospective analysis of the FIRE-3 trial data, the combination of cetuximab plus FOLFIRI, was shown to significantly improve the overall response rate (ORR) in patients with *BRAF*-mutated mCRC compared to bevacizumab plus FOLFIRI (52% versus 40%), although no difference in PFS or OS was noticed.³⁹

In the Phase III study TRIBE, *BRAF*-mutated mCRC patients treated with 5-FU, leucovorin, irinotecan (FOLFOXIRI) plus bevacizumab showed a trend towards improved OS with 19.0 months compared with 10.7 months (hazard ratio [HR] 0.54, 95% confidence interval [CI] 0.24–1.20) and PFS (HR 0.57, 95% CI 0.27–1.23) compared with FOLFIRI plus bevacizumab among the 28 patients with *BRAF* mutation.¹⁶ FOLFOXIRI plus bevacizumab, however, significantly increases the incidence of grade 3 or grade 4 adverse events (AEs) in mCRC patients compared to FOLFIRI plus bevacizumab.¹⁷

Novel combination approaches

BRAF-mutated mCRC is resistant to single-agent RAF inhibitor, such as vemurafenib, with a low ORR of around 5%.^{40 41} Dual *BRAF* plus MEK inhibition does not provide substantial activity either.⁴²

A 35% response rate observed in a Phase Ib study combining vemurafenib with irinotecan and cetuximab in patients with *BRAF*-mutated metastatic colorectal cancer and advanced cancers led the Southwest Oncology Group to set up a randomized controlled trial in *BRAF*^{V600E} mutant mCRC, evaluating irinotecan plus cetuximab with or without vemurafenib.⁴³ Median PFS was 4.4 vs 2.0 months (HR 0.42; 95% CI 0.26–0.55; P<0.001) and response rates were 16 vs 4% (P=0.09) while 67% achieved disease control, compared to 22% for the three-drug regimen versus the two-drug regimen. Safety was regarded as manageable however neutropenia, anemia and nausea occurred more frequently in the arm that included vemurafenib.⁴⁴

Cancer cells with *BRAF* mutations are highly dependent on MEK/ERK signaling. Recent studies have focused on novel targeted therapy combinations to produce more durable responses to *BRAF* inhibitor. An in vitro study suggested that the combination of *BRAF* and EGFR could produce sustained suppression of MEK-dependent activation of mitogen activated protein kinase signaling and overcome EGFR-driven resistance.⁴⁵ Preliminary results from several clinical trials evaluating the combination of *BRAF* and EGFR inhibitors suggest response rates ranging from 4% to 23%.^{32 42 46–49}

The Phase III BEACON CRC, is a randomized, open label, 3-arm study with the objective to evaluate the combination of encorafenib, and cetuximab with or without binimatinib vs FOLFIRI, or irinotecan plus cetuximab as controls, in patients with BRAF^{V600E} mCRC whose disease has progressed after 1 or 2 prior regimens in the metastatic setting.

In this randomized clinical trial, 665 patients with BRAF V600E–mutant metastatic colorectal cancer that had progressed after one or two prior regimens in the metastatic setting were randomized to receive encorafenib/binimatinib/cetuximab, encorafenib/cetuximab, or the investigator’s choice of irinotecan or leucovorin, fluorouracil, and irinotecan (FOLFIRI) and cetuximab.

The treatment combination resulted in a median overall survival of 9.0 months (95% confidence interval [CI] = 8.0–11.4 months) in patients treated with the triplet compared to 5.4 months (95% CI = 4.8–6.6 months) for the control regimens (hazard ratio = 0.52, 95% CI = 0.39–0.70; $P < .0001$). The objective response rate for the targeted triplet therapy was 26%, compared to 2% for the controls. The triplet combination was generally well tolerated with no unexpected toxicities. Grade 3 or higher adverse events were seen in 58% of patients on triplet treatment, 50% of those in the doublet group, and 61% of those in the standard therapy group.

50

Data from the BEACON CRC trial are being used to support regulatory approval of the triplet combination in BRAF V600E–mutant metastatic colorectal cancer, and BRAF inhibitor–based treatment has recently been included as a treatment option in the National Comprehensive Cancer Network© (NCCN©) Guidelines for colon and rectal cancers in the United States.

In light of the early clinical data of the Phase III BEACON CRC study, a Phase II, open label, single-arm, multi-center study, the ANCHOR CRC study, is currently ongoing to evaluate the antitumor activity of the Triplet combination of encorafenib, binimatinib and cetuximab by assessing the confirmed ORR in adult subjects with previously untreated BRAF^{V600E} mutant mCRC, where a total of 90 subjects will be enrolled and the study treatment will be administered in 28-day cycles until disease progression, unacceptable toxicity, withdrawal of consent, initiation of subsequent anticancer therapy or death. After discontinuation of the study treatment, subjects will be followed for survival until 1 year after the start of the treatment of the last subject enrolled.

STUDY RATIONALE

The presence of a BRAF^{V600E} mutation is considered a marker of poor prognosis in patients with mCRC, and findings from clinical trials have largely remained inconclusive regarding the efficacy of first-line treatment options for BRAF^{V600E} mutant mCRC patients. In the absence of a targeted/specific treatment for BRAF^{V600E} mutant mCRC, treatment practices can vary based on local practices and guidelines. There is, therefore, an unmet need to document the current practices for first-line treatment of BRAF^{V600E} mutant mCRC, and their effectiveness and safety in a real-world setting.

This real-world, multicenter, non-interventional study (NIS) will describe the treatment patterns, effectiveness and safety of current treatment regimens of BRAF^{V600E} mutant mCRC patients in Europe, with the aim to put the clinical study findings of the ongoing Phase 2, single-arm, open label trial (ANCHOR) into context of the current treatment landscape excluding investigational therapies. Additionally, the NIS output may be used to support future health technology assessment submissions and publications.

2 STUDY OBJECTIVES

2.1 PRIMARY OBJECTIVE

The primary objective is to describe first-line treatment patterns in BRAF^{V600E} mutant mCRC patients.

2.2 SECONDARY OBJECTIVES

The secondary objectives are:

1. To describe the baseline demographic and clinical profiles of BRAF^{V600E} mutant mCRC patients receiving first-line treatment, overall and by treatment regimen
2. To describe PFS in BRAF^{V600E} mutant mCRC patients receiving first-line treatment, overall and by treatment regimen
3. To describe OS in BRAF^{V600E} mutant mCRC patients receiving first-line treatment, overall and by treatment regimen
4. To describe treatment response in BRAF^{V600E} mutant mCRC patients receiving first-line treatment, overall and by treatment regimen
5. To describe treatment duration (i.e., time from treatment initiation to treatment cessation) in BRAF^{V600E} mutant mCRC patients receiving first-line treatment, overall and by treatment regimen
6. To describe BRAF mutation testing procedure and timing in regards with the first-line treatment in BRAF^{V600E} mutant mCRC patients
7. To describe the frequency of relevant AEs in BRAFV600E mutant mCRC patients receiving first-line treatment, overall and by treatment regimen. Relevant AEs are defined as AEs leading to first-line treatment switch, dose adaptation or discontinuation, or leading to death.

2.3 EXPLORATORY OBJECTIVES

The exploratory objectives are:

1. To describe the reason(s) for treatment discontinuation or switch in BRAF^{V600E} mutant mCRC patients starting first-line treatment
2. To describe the treatment(s) received, by line of treatment (LOT), after first progression in BRAF^{V600E} mutant mCRC patients

3 RESEARCH METHODS

3.1 STUDY DESIGN

This retrospective, multicenter longitudinal study will be conducted in Europe to characterize the treatment patterns, effectiveness and safety of current treatment regimens in BRAF^{V600E} mutant mCRC patients. The observation period is earlier than the date of inclusion of the patient in the study and the study will not provide or recommend any treatment or procedure; patients will continue to be treated as per the routine practice.

For eligible patients, relevant data will be abstracted from their medical records and entered into a centrally-designed electronic case report form (eCRF) in anonymized form. No additional clinic visits

or examinations, laboratory tests or procedures are mandated or recommended as part of this study. Treatment patterns, effectiveness and safety outcomes will be collected using data generated as part of the routine clinical practice.

This multicenter, non-interventional study entails review of medical records of adult patients who initiated first-line treatment for mCRC between January 1st, 2016 and December 31st, 2018 (both dates inclusive) and with a diagnosis of BRAF^{V600E} mutant mCRC discovered a priori or a posteriori to first-line treatment initiation. The target countries for patient enrollment will include Germany, France, Italy, UK, Spain, Belgium, Austria and the Netherlands. Approximately 300 adult patients (≥ 18 years) from a mix of academic and non-academic sites will be enrolled.

In order to obtain a representative sample of real-world patients undergoing treatment for BRAF^{V600E} mutant mCRC in Europe, an evidence-based approach will be adapted to (1) find and select sites within a country that meet the right criteria for success and for representability (taking into account various site-level factors such as center type [public/private, academic/non-academic], center size, center practice, etc.), and (2) identify and mitigate risks that could impact patient enrollment. A strategy plan for site selection will be created to ensure site representativeness, and will describe all processes related to the representativeness survey. The site survey involving a large number of centers managing CRC patients will be conducted prior site selection.

A Scientific Committee will regularly oversee the conduct of the study to provide scientific advice and guidance with regard to the study methodology, study results and related communication.

3.2 POPULATIONS

3.2.1 Source population (if applicable)

Not applicable.

3.2.2 Study population

The study population will include mCRC patients harboring a BRAF^{V600E} mutation determined by a local assay at any time during the disease management, residing in one of the target countries (see Section 3.1 for target countries) and initiating first-line treatment between January 1st, 2016 and December 31st, 2018 (both days inclusive).

3.2.2.1 **Inclusion criteria**

Patients will be eligible for inclusion if they fulfil all of the following criteria:

- Male or female aged ≥ 18 years at diagnosis of mCRC
- Diagnosis of histologically or cytologically confirmed CRC that is metastatic and unresectable
- Presence of BRAF^{V600E} mutation in tumor tissue, as confirmed by a local assay

- Initiated first-line treatment with drugs registered for mCRC in the respective country at the time of treatment between January 1st, 2016 and December 31st, 2018 (both days inclusive)
- Provision of informed consent or non-opposition to the patient (or next of kin, if applicable) for the use of data, according to local regulations

3.2.2.2 Exclusion criteria

Patients will be excluded from the study if they fulfil any of the following criteria:

- Patients with another concomitant cancer at the time of diagnosis*
- Patients participating in interventional trials on investigational drugs at the time of initiation of first-line treatment

* Except for non-metastatic non-melanoma skin cancers, or in situ or benign neoplasms; a cancer will be considered concomitant if it occurs within 5 years of mCRC diagnosis.

For patients who fulfil the eligibility criteria, but do not participate in the study (non-consent, non-inclusion because of patient selection process), a screening log will be maintained (subject to local regulations) to record the reason for non-participation, gender, age at diagnosis (pre-defined categories), first line treatments received (if available) and survival status.

3.2.3 Participants recruitment and follow-up

3.2.3.1 Participant selection process

In each participating center, all eligible patients' medical records will be identified. The following steps will be followed for patient selection:

- Participating sites (wherever feasible) will be asked to list exhaustively all eligible patients in an pseudonymized way
- The pseudonymized patient list will then be given a number of enrollment
- Medical records will be abstracted by the site staff until reaching the targeted number of patients per site or reaching the end of the list
- The patient will be informed of this data collection according to applicable regulations. If the patient has opposed to data collection, the reason will be noted and the next record from the enrollment list will be identified.

3.2.3.2 Participant data collection

Patients data will be collected from the start of first-line treatment for mCRC until the end of the observation period (date of death or last day of study observation period, ie. January 31st, 2020). Patients lost to follow-up will be censored at the date of their last available medical record or the date when they were last known to be alive. The data will be anonymized during the entry into the eCRF by using an algorithm which generates a random patient number without any indication of the patient, centre or country. This anonymization will be maintained in the database used for statistical analysis.

3.3 STUDY OUTCOMES

3.3.1 Primary endpoint

The primary endpoints are first-line SACT treatment patterns in BRAF^{V600E} mutant mCRC patients, described by:

- Agent or combination of agents received
- Duration of treatment
- Maintenance therapy (if any)

The first-line SACT regimen(s) will be described from the time of treatment initiation (for mCRC) until the time of first documented disease progression, treatment discontinuation or switch, whichever is earlier.

LOT definition will be connected to treatment progression. The LOT will be defined using a data-driven approach. In the SAP an algorithm for LOT definition will be specified, which will consider the specific treatment(s) received (stop and start dates), progression (as recorded in the patient medical record, including date), documented reasons for discontinuation of treatments and gap(s) between subsequent treatment regimens.

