All medical data will be confidential. Pierre Fabre Medicament (PFM), as the Sponsor of the study and data controller, is responsible for the processing of personal data in accordance with the provisions of Regulation 2016/679/EU of the European Parliament and of the Council of 27 April 2016 on the protection of natural persons with regard to the processing of personal data and the free movement of such data (GDPR), the data collected being for research purposes in the field of health, the legal basis of the processing being the legitimate interest of the data controller.

Safety

Within the timeframe of study documentation/data collection, Pierre Fabre has not registered any drug used for the treatment of mCRC, therefore no Pierre Fabre-owned drug was authorized for use within clinical routine treatment for mCRC or BRAF^{V600E}-mutant mCRC. Moreover, patients treated in the frame of interventional clinical studies for mCRC and patients treated with concomitant systemic therapies for cancers other than mCRC, will be excluded. Therefore, this NIS is not expected to generate any safety reports with regard to Pierre Fabre-owned drugs within the frame of the eligibility criteria.

Irrespective of this retrospective anonymized data retrieval, the participating physicians will be reminded of their general reporting obligations with regard to adverse drug reactions concerning any Pierre Fabre product or drugs of other manufacturers in accordance with the respective national law and regulations.

Study endpoints

Primary endpoint

First-line SACT treatment patterns in BRAF^{V600E} mutant mCRC patients, described by:

- Agent or combination of agents received
- Duration of treatment
- Maintenance therapy (if any)

The first-line SACT regimen(s) will be described from the time of treatment initiation (for mCRC) until the time of first documented disease progression or treatment discontinuation, whichever is earlier.

LOT definition will be connected to treatment progression. The LOT will be defined using a data-driven algorithm; in the Statistical Analysis Plan (SAP) an algorithm for LOT definition will be specified, which will consider the specific treatment(s) received (stop and start dates), progression, tumor response (as recorded in the patient medical record, including date), documented reasons for discontinuation of treatments and gap(s) between subsequent treatment regimens, and will be further elaborated in the protocol and the SAP.

Secondary endpoints

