3.3.2 Secondary endpoints

1. Description of the demographic and clinical profile of patients at the time of treatment initiation (for mCRC)
2. PFS, defined as the length of time between initiation of first-line treatment for mCRC and the first documented disease progression (if disease progression is not well documented in a patient's medical record, then the start of the subsequent LOT may be considered as proxy for disease progression) or death (whichever is earlier)
3. OS, defined as the length of time between first-line treatment initiation (for mCRC) and death (due to any cause)
4. ORR, defined as complete response (CR) or partial response (PR), described at the end of first-line treatment for mCRC
5. Time to treatment cessation, defined as the length of time between initiation of firstline treatment for mCRC and documented disease progression (or start of subsequent LOT, if disease progression is not well documented in the patient medical record), treatment discontinuation or switch to another treatment (defined as change from 1 treatment regimen to another treatment regimen, e.g. change from FOLFOX-based regimen to FOLFIRI or irinotecan-based regimen)
6. Time to BRAF mutation testing since mCRC diagnosis and since first-line treatment for mCRC, and description of testing procedures
7. Frequency of relevant AEs during first-line treatment for mCRC. Relevant AEs are defined as AEs leading to first-line treatment switch, dose adaptation or discontinuation, or leading to death.

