3.3.3 Exploratory endpoints

1. Description of reasons for treatment discontinuation or switch at the end of first-line treatment for mCRC
2. Second (and subsequent) line treatment patterns in BRAF^{V600E} mutant mCRC patients, defined as treatments received after disease progression following first-line treatment, and described by:
 - Agent or combination of agents received
 - Duration of treatment

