3.3.4 Exposure definition and measurement

This is a NIS of real-world treatment practices in the adult BRAF^{V600E} mutant mCRC patient population. This protocol does not recommend the use of any specific treatments, and no study medication will be provided as part of participation in the study.

The exposure of interest will be the first-line SACT (monotherapy, doublet therapy, or triplet therapy with or without a targeted therapy [either VEGF inhibitor or EGFR inhibitor]) for the treatment of BRAF^{V600E} mutant mCRC. Treatment patterns will be described by LOT.

Line of therapy will be defined as follows:

- First LOT: the start of first LOT will be defined as the first administration of SACT therapy after diagnosis of mCRC to the date of first documented disease progression
- Second and subsequent LOTs: mCRC treatment(s) received on or after the date of documented disease progression following previous LOT to the date of documented disease progression on or after the current LOT
- In the absence of information on disease progression, an algorithm will be specified in the SAP based on the specific treatment(s) received (stop and start dates), progression (as recorded in the patient medical record, including date), documented reasons for discontinuation of treatments and gap(s) between subsequent treatment regimens.

The exposure variables of interest are described in Table 1.

Table 1 Study Exposure

Exposure	Definition and Measurements
Systemic anti-cancer therapy (SACT) ¹ for mCRC	
 Details on SACT (by LOT) 
 LOT² (e.g., first, second, third, etc.) Type of treatment³ (i.e., monotherapy, doublet therapy, triplet therapy) Agents used 
 Chemotherapy regimens (e.g., FOLFOX, FOLFIRI, FOLFOXIRI) Targeted agents (e.g., bvacizumab, cetuximab, panitumumab) Duration of treatment: start date and stop date Date of documented progression Dates and reasons for treatment alteration (e.g., switch, discontinuation, dose escalation/reduction) Maintenance therapy (if any) of first line treatment: name of agent(s); start date and stop date Treatment response (as recorded in patient medical record by the treating physician) of first-line treatment of mCRC: type of response (CR, PR, PD); date recorded

¹ All SACT treatments received/prescribed for mCRC will be captured.

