3. Observational period: patients will be followed from the start of first-line treatment for mCRC and followed until the end of the observation period. Patients lost to follow-up will be censored at the date of their last available medical record or the date when they were last known to be alive.
4. Data to be collected at the time of mCRC diagnosis.
5. Data to be collected at the time of initial diagnosis of mCRC/CRC.
6. Information on routine laboratory tests will be collected at the time of mCRC diagnosis; information on other tests (including BRAF mutation) and assessments can be captured throughout the observation period.
7. Data on number of treatment cycles and maintenance therapy to be collected for first-line therapy only.
8. Data to be collected for first-line therapy only.

AE: adverse event; CR: complete response; CRC: colorectal cancer; ECOG: Eastern Cooperative Oncology Group; mCRC: metastatic colorectal cancer; NIS: non-interventional study; PD: progressive disease; PR: partial response; TNM: Tumor, Node, Metastasis.

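### First-line treatment has three different end rules; under 3.3.1 a regimen begun after a non-progression switch falls outside both the primary and second-line descriptions, and the place of maintenance is unstated

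*Combined protocol and SAP*

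**What the plan says.** The protocol gives three ends for first-line treatment:

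- **Section 3.3.1 (primary endpoint):** regimens are described from initiation "until the time of first documented disease progression, treatment discontinuation or switch, whichever is earlier".
- **Synopsis (primary endpoint):** "until the time of first documented disease progression or treatment discontinuation, whichever is earlier". Switch is not named.
- **Section 3.3.4 (exposure):** first LOT runs from the "first administration of SACT therapy after diagnosis of mCRC to the date of first documented disease progression".

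The definitions that interact with these rules are:

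- **Switch:** section 3.3.2, item 5, ends time to treatment cessation at progression, discontinuation or "switch to another treatment (defined as change from 1 treatment regimen to another treatment regimen". The definition continues with an example, a FOLFOX-based regimen changed to FOLFIRI or an irinotecan-based one. Table 2 uses the same event.
- **Second and later lines:** section 3.3.3 describes these as "defined as treatments received after disease progression following first-line treatment". Section 3.3.4 also requires progression, and section 3.8.4 restricts the analysis to patients who progressed.
- **Maintenance:** the synopsis and 3.3.1 name it as the third descriptor of the primary endpoint. Table 1 lists "Maintenance therapy (if any) of first line treatment: name of agent(s); start date and stop date" as an item separate from treatment alteration. Table 4, footnote 7, adds "Data on number of treatment cycles and maintenance therapy to be collected for first-line therapy only". Section 3.8.2 summarises it in the primary analysis with regimen and duration.

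The LOT algorithm is deferred to the SAP. Section 3.3.4 invokes it only where progression information is absent. The synopsis and 3.3.1 state no such limit. The algorithm itself is not set out in the document reviewed.

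**The concern.** The three rules can give different first-line durations and regimen descriptions from the same chart, and the text gives none of them precedence. Two groups are exposed: patients who change regimen without progressing, and patients who step down to maintenance or restart after a break. Time to treatment cessation inherits the question through the switch event, and the count of adverse events during first-line treatment depends on where first line ends. The study is meant to put a single-arm first-line trial into context and may support health technology assessment, so first-line duration and maintenance use should not depend on which paragraph the programmer follows.

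**Working it through.** **1. The plan's own figure.** The only number attached to the primary endpoint is the precision in section 3.5. The half-width is 1.96 × √(p(1−p)/n). With n = 300 this gives 2.47%, 3.39% and 4.53% at p = 5%, 10% and 20%, matching the stated ±2.5%, ±3.4% and ±4.5%. All 45 cells of Table 5 reproduce to rounding. The precision arithmetic is not in dispute; the question is what is being measured.

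**2. The rules applied to the same patients.** Treatment starts at time 0, something other than progression happens at time *a*, and progression is documented at a later time *b*.

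| Event at *a* | Window closes, 3.3.1 | Window closes, synopsis | First LOT ends, 3.3.4 | Second line opens |
|---|---|---|---|---|
| Change to a different regimen | *a* | *a* if the change counts as discontinuation, otherwise *b* | *b* | *b* |
| Step-down to maintenance | *a* if it counts as switch or discontinuation, otherwise *b* | *a* if it counts as discontinuation, otherwise *b* | *b* | *b* |
| Stop, then restart before *b* | *a* if the break counts as discontinuation | same | *b*, with drug-free time inside | *b* |

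Row 1 needs no interpretation of 3.3.1. The new regimen, given between *a* and *b*, is outside the primary window and outside second line, but inside first LOT. Rows 2 and 3 turn on a classification that no section supplies.

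**3. Size, as illustration only.** The documents contain no switch, step-down or induction figures. The only anchor is the median first-line PFS of 5.4 and 6.4 months quoted in the background, used here as a stand-in for time to the end of the line, with exponential times assumed.

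*(a) Any exit without progression.* Let a share *s* leave the initial regimen before progression, with competing exponential hazards. If the progression hazard is λ, the total hazard is λ/(1−s), so the median under 3.3.1 is (1−s) times the median under 3.3.4.

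| Assumed *s* | From 5.4 months | From 6.4 months | Patients of 300 |
|---|---|---|---|
| 10% | 4.9 | 5.8 | 30 |
| 20% | 4.3 | 5.1 | 60 |
| 30% | 3.8 | 4.5 | 90 |
| 50% | 2.7 | 3.2 | 150 |

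*(b) Step-down at a fixed time, if it closes the window.* Assume induction of *t* = 4 or 6 months and that 30–70% of those still progression-free step down.

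- **Share closed:** s × 0.5^(t/m), where *m* is the median. This runs from 0.3 × 0.5^(6/5.4) = 0.3 × 0.463 = 14% to 0.7 × 0.5^(4/6.4) = 0.7 × 0.648 = 45%.
- **Mean:** m/ln 2 is 7.8 to 9.2 months. Multiplying by (1 − share closed) gives 7.79 × (1 − 0.7 × 0.598) = 4.5 to 9.23 × (1 − 0.3 × 0.522) = 7.8 months.
- **Median, t = 4:** survival just before 4 months is 0.598 to 0.648. Removing even 30% takes it to 0.419 to 0.454, so the median is 4.0 in every case.
- **Median, t = 6:** with m = 5.4, survival at 6 months is already 0.463 and the median stays at 5.4. With m = 6.4 it moves from 6.4 to 6.0.

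The effect on the median under (b) therefore runs from none to 2.4 months (6.4 − 4.0), decided by an induction length that the documents do not give.

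**The case against.** **Maintenance.** A reader might infer that the primary endpoint cannot contain maintenance. The documents do not support that. Table 1, Table 4 footnote 7 and section 3.8.2 treat it as part of first line, Table 1 keeps it apart from switch and discontinuation, and the example of a switch is a change of chemotherapy backbone. An analyst following 3.8.2 would report it. What stands is that 3.3.1 and 3.3.2 make no exception for step-down, so the literal reading remains open.

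**Post-switch regimens.** A reader might also infer that these are reported nowhere. Section 3.3.4 says patterns are described by LOT and keeps such regimens in the first, Table 1 captures all systemic treatment, the wording of 3.3.1 allows for more than one regimen, and reasons for switch are an exploratory endpoint. The narrower statement stands: under the 3.3.1 window, read with 3.3.3, they belong to neither description.

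**Different concepts.** A line lasting to progression and a regimen ending at stop or switch can coexist, and ending time to treatment cessation at a regimen change is a legitimate choice. But the protocol does not say that two concepts are intended, and the synopsis and 3.3.1 state the same endpoint differently.

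**The SAP.** It may settle part of this, and its algorithm cannot be judged from the document reviewed. It would be wrong to say that it cannot help. However, 3.3.1 states the window separately from the LOT definition, and 3.3.4 confines the algorithm to patients without progression information.

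**Size.** Quoting only the drop to a 4.0-month median would mislead, since 6-month induction gives a shift of 0 to 0.4 months.

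**Conclusion.** The point holds in limited form. The synopsis, 3.3.1 and 3.3.4 give three different ends for first-line treatment. Under 3.3.1, a regimen begun after a non-progression switch is outside the primary window and not in second line, while 3.3.4 counts it as first line. The place of maintenance is undefined: a literal reading could close the window, and time to treatment cessation, when maintenance starts, in conflict with its being a primary-endpoint element. This is more than missing detail, because stated rules conflict on the primary endpoint.

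The size cannot be derived from the documents. The illustrations assume exponential times, PFS medians as a proxy for line length, and shares and induction lengths chosen for range; the mean is more sensitive than the median, which may barely move. The precision in section 3.5 is unaffected. The inconsistency should be resolved in the protocol and SAP before database lock.

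**What to change.** - **One end rule:** use the same end of first line in the synopsis, 3.3.1, 3.3.4 and Table 2, namely the 3.3.4 definition, with the SAP algorithm where progression is not documented.
- **Phases within the line:** describe initial regimen, maintenance and any non-progression switch as successive phases of first line, and state how a break followed by a restart is classified.
- **Time on drug kept separate from line length:** compute duration of treatment from the recorded start and stop dates of each phase. Otherwise a progression-based line would count drug-free time as treatment.
- **Time to treatment cessation:** state that step-down to maintenance is not a switch event for this endpoint, and report time to the end of the initial regimen separately.

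The cost is protocol and SAP wording plus one derived phase variable. Table 1 already collects agents, start and stop dates, maintenance agents and dates, and dates and reasons for treatment alteration, so no new data are needed.
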